7. STUDY PROCEDURES

a. Recruitment, Randomization, treatment allocation, and blinding

A standardized, IRB approved email will be sent to department chairs describing the study. A research coordinator will reach out to interested participants via phone with the help of an IRB-approved verbal script to introduce the study, confirm eligibility and provide further instructions on how to access and sign the IRB-approved ICD via REDCap using their own electronic devices. It is important that we obtain the consent via REDCap to a) avoid direct person-to-person contact and comply with social distancing imposed recommendations, and b) minimize the waste of reconstituted BCG by allowing the research personnel to schedule vaccinations in a controlled fashion.

A person under investigation for COVID is not eligible, as per eligibility criteria. To further prevent risk of nosocomial transmission in case of asymptomatic shedding, consenting and screening will occur electronically and over telephone and the intervention will occur at a designated research location away from patient care. If a study participant develops symptoms of COVID19 after enrollment in the study, they will be tested for COVID19 like any other health care worker or community member, and under the supervision, provisions and regulations of their institution and followed per protocol.

Patient registration into the trial will happen immediately after consent has been provided and will involve entering of baseline information into an electronic data capture system (RedCap).

Once the eligibility is confirmed and the ICD signed by the participant and stored in REDCap, the research coordinator will randomize the participant and communicate the treatment assignment to the nurse administering the vaccination. The nurse will subsequently assign an appointment and communicate date and time of vaccination with the participant. All eligible participants will receive intradermal injections of BCG:placebo in a 1:1 ratio.

Both participants and investigators will be blinded to the treatment assignments during the study. However, in case of an emergency where it is important to know the treatment received, the investigator and/or participant can reach out to the unblinded study personnel who will provide the unblinded data. All participants will receive their treatment allocation at the end of the study, after the data analysis is finalized.

Unblinded personnel will not be involved in the collection and analysis of study data other than the baseline eligibility criteria.

The end of the study is defined as the last patient's last entry in the electronic data capture system.

Informed Consent and Eligibility

The following types of procedures will be conducted as indicated below:

Medical history will be obtained from patient medical record/clinical chart. Informed Consent will be obtained to access these records. When information cannot be obtained or is not available from the patient medical record/clinical chart, it will be obtained via patient interview.

Visual examination will be conducted solely to look for existing BCG vaccination scars.

Symptom evaluation will be conducted via an electronic survey administered to participants every 7 days.

Height, weight, HIV status **and pregnancy** status will be collected as self-reported information. If unknown, a urine pregnancy test will be performed.

Nasopharyngeal, oral and/ or rectal **swabs** will be collected for rt-PCR test for SARS-CoV2 infection if a participant develops symptoms consistent with Covid-19.

If a participant does not know their PPD/IGRA status from within the last 24 months (all health care providers should have this information), an IGRA can be performed to evaluate eligibility.

Study participants have the option of donating blood via phlebotomy (for serological test for Covid-19 disease and PBMCs for immune correlates) or providing a fingerstick and dried blood spot (for serologic test for Covid-19).

Data will be collected at four time points/periods: (1) after consent, (2) at baseline, (3) during follow-up period, and (4) at study end.

Data to be collected during screening includes medical history, visual exam results, results of rt-PCR and serological test results.

Data to be collected during baseline enrollment includes eligibility confirmation, demographic information, risk factors, randomization assignment, confirmation of BCG vaccination/placebo, any immediate reactions to BCG vaccination/placebo. Subjects may also be asked to share a picture of just the injection site. Sharing the picture of the injection site is optional and will not be available to blinded staff members until the end of the study.

Data to be collected during follow-up includes intermittent surveys about the presence of flu-like symptoms, rt-PCR test results if done, serological test results, if testing positive for Covid-19 information regarding their disease course, and disease outcome status.

The following procedures will be performed and/or data collected as listed below data after informed consent is obtained:

Data Variable	
Date of signed Informed Consent Form	X
Role in hospital	X
Department in hospital	X
rt-PCR test for SARS-CoV2 result	X
Serological test for Covid-19 result	X
Number of BCG scars (by visual examination)	X
Medical history*	X
Previous PPD and IGRA test results	X
History of TB disease	X
History of previous HIV testing	X
Urine Pregnancy test result (if applicable)	X
Plans of pregnancy in 30 days	X
Plan to stop working in 3 months/ leave facility in 6 months	X
Current diabetes mellitus	X
Current chronic kidney disease	X
Currently taking immunosuppressive drugs	X

Living with someone with HIV, immunocompromised, taking immunosuppressive drug	X
Chemotherapy in past 3 months	X
History of organ/bone marrow transplant	X
Access to smartphone	X

b. Baseline data collection/procedures

The following procedures will be conducted and data collected as indicated below:

A questionnaire to obtain information about age, sex, demographic information, who they live with, smoking status, any current medications they are on, and other comorbidities

Participants will then be randomized to either receive a single dose of BCG vaccination or placebo.

BCG vaccination or placebo will be administered.

Eligibility screening data will carry forward into the trial.

The following additional data points will be collected:

Data Variable	
Age	X
Sex	X
Race	X
Ethnicity	X
Nationality	X
Who they live with	X
Height	X
Weight	X
Smoking status/tobacco use	X
Alcohol use	X
Current list of medications	X
Current list of comorbidities	X
History of diabetes mellitus	X
History of hypertension	X
History of stroke	X
History of kidney disease	X
History of COPD	X
Randomization assignment	X
BCG/placebo administered	X

c. Follow-up procedures and data collection:

Participants will be followed to assess whether they get infected with SARS-CoV2:

Participants will complete intermittent surveys via an electronic system every 7 days to assess the presence of any flu-like symptom, including sore throat, fever, headache, malaise, and cough. Note that this is part of routine surveillance for Covid-19 in health workers at the United States site. Consent forms will ask for consent to access this survey information.

Any positive response on the survey will trigger a nasopharyngeal, oral and/ or rectal swab to be collected to test for Covid-19 via rt-PCR

All participants, regardless of survey responses, will have serology for Covid-19 tested at 4 week intervals during the follow-up period (6 months)

If a participant completes the follow-up period and does not test positive for disease, their study participation is complete

If a participant does test positive for disease, their disease status will be ascertained for up to two months or until an outcome is available through one of the following mechanisms: (1) an electronic survey if they are not admitted to the hospital, including questions about the number of days they are ill, daily fever, and other symptoms; or (2) if they are admitted to the hospital, ordinal outcomes for disease severity will be extracted from the hospital's electronic medical records system.

During the first week of follow-up, all participants will actively be asked about any adverse events; thereafter, participants will report unsolicited AEs through the electronic survey. Vaccine related adverse events will be graded using the FDA guidance (<https://www.fda.gov/media/73679/download>) and noted using WHO-recommended Adverse event following Immunization forms (AEFI; <https://vaccine-safety-training.org/classification-of-aefis.html>).

Participants will have the option of donating 12 mL of blood for plasma (serology) and PBMCs for secondary analysis of immune correlates and for future analysis based on covid19-specific IgM and IgG. If they do not donate 12mL of blood, a fingerstick will be required for baseline COVID19 serology.

Dried Blood Spot (DBS): all participants will self-collect DBS samples at week 4, 8, 12, 16, 20 and 24. Envelopes to store the DBS are provided upon enrollment and can be mailed or dropped off at work and picked up by study coordinators.

COVID specific RNA is found in stool for ~21 days when an individual develops infection (<https://doi.org/10.1038/s41586-020-2196-x>). Participants will have the option of collecting stool swabs monthly if they are asymptomatic or weekly if they develop symptoms. Nucleic acid testing will be performed in retrospect to support secondary objectives.

If participants develop symptoms consistent with COVID19, will be PCR tested for COVID19. They will be given the option of donating 12 mL of blood for plasma and PBMCs 2 weeks after symptoms resolve.

Week 12 (+/- 2 Weeks), participants will be given the option to donate 12 mL of blood for plasma and PBMCs for secondary analysis of immune correlates and for future secondary analysis based on covid-specific IgM and IgG.

Week 24 (+/- 2 Weeks), participants will be given the option to donate 12 mL of blood for plasma and

PBMCs for secondary analysis of immune correlates and for future secondary analysis based on covid-specific IgM and IgG.

Except for the administration of BCG vaccine or placebo and the above mentioned DBS and phlebotomy, participants will undergo no invasive procedures for study purposes.

The following data points will be collected during the follow-up period and at end of study:

Data Variable	
Sore throat (collected at multiple time points)	X*
Fever (collected at multiple time points)	X*
Headache (collected at multiple time points)	X*

Malaise (collected at multiple time points)	X*
Cough (collected at multiple time points)	X*
rt-PCR test for SARS-CoV2 result (as indicated)	X
Serological test for Covid-19 result (every 2 weeks)	X
Number of days ill	X
Daily fever	X
Other Covid-19 symptoms	X
Admitted to hospital	X
Required oxygen	X
Treated in intensive care	X
Required ventilation	X
Death	X
Severe pneumonia	X
Respiratory failure	X
Acute respiratory distress syndrome	X
Sepsis	X
Septic shock	X

**Already being collected as part of routine surveillance of health care workers. Will request access to this information in Informed Consent Form.*

d. Withdrawal of individual subjects/End of Study

Subjects can leave the study at any time for any reason if they wish to do so without any consequences. The investigator can decide to withdraw a subject from the study for urgent medical reasons. Participants who received placebo will be unblinded at the end of the study and pending a recommendation by the DSMB, they will be offered the option of receiving the BCG intervention.

e. Replacement of individual subjects after withdrawal

A participant will only be replaced in case of withdrawal before the administration of BCG vaccine/placebo.

a. Rationale:

A potential additional benefit of BCG vaccination is the impact of the vaccine on improving cognition and Alzheimer's Disease (AD) outcomes in the presence and absence of COVID19. There are series of published evidence that BCG can improve cognitive outcomes for AD and Parkinson's[16, 17]. Furthermore, there is mounting evidence that COVID-19 can impact the CNS[18-21], as evidenced by the loss of smell and taste reported by many patients as well as the presence of dementia in nearly 40% of patients. Prior pandemics have observed spikes in Parkinson's and other cognitive disorders afterwards[22] and coronaviruses have been associated with Parkinson's[23]. The cognition sub-study would involve cognition baseline and MRI (brain imaging) and follow up at 6 months and 2 years and would include BCG vaccinated, placebo-controlled, COVID-exposed and non-exposed groups. This study design will provide an extremely sensitive and longitudinal measure of cognitive ability that will allow examination of the impacts of COVID-19 and vaccination on the trajectory of mental status.

b. Premature termination of the study

During the study, interim analyses is planned. The safety and futility of the trial will be monitored carefully by the study team and DSMB during these interim analyses. If warranted, the study will be terminated (prematurely). Description of the DSMB and interim analysis is described further below.

8. OPTIONAL COGNITIVE SUB-STUDY (Not available at all sites).

a. Population:

400 subjects enrolled in main BADAS study.

b. Additional Inclusion Criteria:

- Normal or corrected-to-normal vision and hearing (able to see images on computer screen and hear auditory events delivered through the computer speaker).
- >45 years of age.

d. Additional Exclusion Criteria:

- Significant history of mental illness, drug or alcohol abuse; severe trauma preventing normal use of dominant hand (needed to move the mouse cursor); clinical depression (unless medically controlled); other neurologic conditions (i.e. stroke), or learning disability; ophthalmologic/visual problems that prevent viewing a computer screen at a normal distance (such as legal blindness, detached retinas, occlusive cataracts).
- Having pacemakers, aneurysm clips, cochlear implants, pulse oximeters, EKG leads, or other metal/foreign objects in body or face, making them unable to receive **MRI**.
- <45 years of age.

e. Study Endpoints (Additional to Main Study):

Primary endpoint: incidence of [COVID-19](#)-related cognitive impairment.

Secondary endpoint: severity of cognitive impairment following BCG vaccination compared to placebo that is COVID-19-related.

f. Additional Risks Beyond Main Study:

Minimal risk, MRI and clinical cognitive tests are minimal risk and only involve a small amount of additional time at each visit, expected to be about 2 h in duration, including MRI, with three visits total.

g. Clinical Cognitive Assessment (CCA):

A rapid and sensitive assessment of cognitive status will be accomplished using a cognitive battery with multiple forms designed to identify subtle changes in high functioning medical staff. We have chosen assessments that reduce human cost and produce low variability in data, minimizing potential error. A computer-based process will be used to accomplish high sensitivity and low variability in our cognitive assessments. We will use the NIH Toolbox Cognition Batteries that have strong psychometric assessment capabilities, appropriate procedural considerations, the ability to integrate with REDCap and utilize tablet computer for the process. This system will minimize human factor and related costs with unlimited administrations and scoring capability. We will utilize the ability of NIH Toolbox to assess integrated higher level aspects of cognition where cognitive changes are most impactful, including: attention, working memory, executive functioning and processing speed measures. This strategy will allow us to identify subtle changes in cognitive function due to COVID-19 and the ability of BCG vaccination to mitigate them.

Details for NIH Toolbox Cognition Batteries are available online:

<http://www.healthmeasures.net/explore-measurement-systems/nih-toolbox/intro-to-nih-toolbox/cognition>

h. Magnetic Resonance Imaging (MRI):

Structural imaging by MRI allows sensitive assessment of most cognitive disorders, a partial list of which includes: dementia, Alzheimer's, Parkinson's, mild cognitive impairment, vascular cognitive impairment, and cerebrovascular disease. When combined with longitudinal imaging, MRI becomes even more sensitive and can establish cognitive status trajectory well before these neuropathologies are clinically obvious[24-26]. Whole brain high-resolution MRI with coronal slices will be used to image the entire brain, hippocampus and temporal lobe to assess the extent of regional atrophy, including volume loss, and cerebrovascular disease using both visual rating scales and automated segmentation methods to measure cognitive changes. Measures will include assessment of vascular dementia, postero-medial parietal lobe atrophy, posterior cingulate gyrus, hippocampal-mediated temporal lobe, atrophy in inferior frontal lobe, visual cortex, insula, hypothalamus, midbrain, caudate, putamen, anterior hippocampi, macrohaemorrhage, fronto-temporal degeneration, atrophy of medial temporal structures and whole-brain atrophy. This strategy will provide a sensitive measure of cognitive status at each time point and trajectory that will ensure we obtain rapid insight into the effects of COVID-19 and BCG vaccination on cognition.

9. SAFETY REPORTING**a. Temporary halt for reasons of subject safety**

The investigators will suspend the study if there is sufficient ground that continuation of the study will jeopardize subject health or safety. The investigator will notify the IRB without undue delay of a temporary halt including the reason for such an action. The study will be suspended pending a further positive decision by the IRB. The investigator ensure that all subjects are kept informed.

b. AEs, SAEs and SUSARs**i. Adverse events (AEs)**

Adverse events are defined as any undesirable experience occurring to a subject during the study, whether or not considered related to the investigational product, the placebo or the trial procedures. Adverse events can be self-reported by the subjects using the mobile application. All adverse events reported spontaneously by the subject or observed by the investigator or his staff will be recorded and assessed per institutional IRB and policies.

ii. Expected mild Adverse events

Although BCG vaccination almost always causes local reactions, serious or long-term complications are rare. Almost all recipients of BCG will experience vaccine site erythema and development of a small pustule. Slight tenderness at the puncture site may be encountered as well as some itching. The initial skin lesions usually appear within 10–14 days and consist of small red papules at the site. The papules reach maximum diameter (about 3 mm) after 3 to 4 weeks, after which they may scale and then slowly subside.

Theoretically it is feasible that a HCW BCG vaccinated could shed attenuated live BCG and transmit this to an immunocompromised patient. While theoretically feasible, we found no case reports of such events. Further, the ability to keep the vaccine site covered is an exclusion criterion. Study participants will be notified of the expected pustule formation and the need to keep it covered by gauze and clothes during the period it is draining. Before the pustule drains, it has characteristic fluctuant appearance and should be covered with gauze from the time fluctuance develops.

iii. Expected rare, serious Adverse events:

Approximately 1 in 1000 to 1 in 10,000 will experience suppurative lymphadenopathy including moderate axillary or cervical lymphadenopathy and induration and subsequent large pustule formation. While local usually resolved within 3-4 weeks, supportive lymphadenopathy can persist for as long as 3-6 months after vaccination. There is not definitive management for suppurative lymphadenitis and treatment will be managed on a case by case basis with some undergoing “watchful surveillance and others drained with incision and drainage. All adverse events will be discussed by the site and overall PIs.

More serious local reactions include ulceration at the vaccination site, regional suppurative lymphadenitis with draining sinuses, and caseous lesions or purulent draining at the puncture site. These manifestations might occur up to 5 months after vaccination and could persist for several weeks. The intensity and duration of the local reaction depends on the depth of penetration of the multiple puncture device and individual variations in patients' tissue reactions.

The most serious complication of BCG vaccination is disseminated BCG infection. The most frequent disseminated infection is BCG osteomyelitis (0.01 to 43 cases per million doses of vaccine administered) which usually occurs 4 months to 2 years after vaccination. Fatal disseminated BCG infection has occurred at a rate of 0.06–1.56 cases per million doses; these deaths occurred primarily among immunocompromised persons. Disseminated BCG will be treated and managed by each site PI and treated with antibiotics (rifampicin, isoniazid, ethambutol). The risk of anaphylaxis to BCG has been described but is very rare. In a study of over 50,000 individuals who received BCG or placebo, anaphylaxis occurred in no individuals receiving BCG.[27] The vaccination will take place within 0.5 mile of a hospital in the event this occurs. There is nowhere in the TMC area that would not therefore be suitable.

Theoretically, it is feasible that BCG could induce an enhanced innate immune response that induces exuberant immune pathology when an individual is secondarily infected with covid19. Existing human and animal models suggest that BCG will improve antiviral immunity and not induce immunopathology. A recent report in the Lancet suggests that covid related disease is due to suppressed immunity, not due to exuberant immunopathology (Wang To et al [https://doi.org/10.1016/S1473-3099\(20\)30196-1](https://doi.org/10.1016/S1473-3099(20)30196-1) Chen and Li, Lancet ID: [https://doi.org/10.1016/S1473-3099\(20\)30235-8](https://doi.org/10.1016/S1473-3099(20)30235-8)), but high viral load and lack of host immunity. Participants will be completing daily symptom dairies and results will be reviewed every 4 weeks by a DSMB consisting of immunology, pulmonology, and infectious disease physicians. In personal correspondence from [name] (letter available upon request), he reports anecdotal evidence that BCG does not induce an increase in viral infections. Further, in the ACTIVATE trial, which took place this past year, 200 elderly patients in Greece upon hospital discharge received either BCG vaccination or placebo. None have since developed a covid-related ARDS response (letter from [name] and email from [name] available upon request.)

iv. Serious adverse events (SAEs)

An adverse event or suspected adverse reaction is considered “serious” if, in the view of either the investigator or the sponsor, it results in any of the following outcomes:

- Death
- A life-threatening adverse drug experience – any adverse experience that places the patient, in the view of the initial reporter, at immediate risk of death from the adverse experience as it occurred. It does not include an adverse experience that, had it occurred in a more severe form, might have caused death.
- Inpatient hospitalization or prolongation of existing hospitalization

- A persistent or significant incapacity or substantial disruption of the ability to conduct normal life functions.

Important medical events that may not result in death, be life-threatening, or require hospitalization may be considered a serious adverse drug experience when, based upon appropriate medical judgment, they may jeopardize the patient or subject and may require medical or surgical intervention to prevent one of the outcomes listed in this definition. Examples of such medical events include allergic bronchospasm requiring intensive treatment in an emergency room or at home, blood dyscrasias or convulsions that do not result in inpatient hospitalization.

All events occurring during the conduct of a protocol and meeting the definition of a SAE must be reported to the IRB per their policy and institutional guidelines .

v. Suspected unexpected serious adverse reactions (SUSARs) / Unanticipated Problems (UP)

- UPs are defined according to each institutional IRB of record. The UP will be defined and reported per institutional policy. All serious adverse events will be reported to local site PI within 24 hours of knowledge of the event.
- Unless stated otherwise in the protocol, all SAEs, expected or unexpected, will be reported to the DSMB as soon as possible, but in all cases within 5 working days of knowledge of the event regardless of the attribution.
- Death or life-threatening events that are unexpected, possibly, probably or definitely related to drug must be reported within 24 hours of knowledge of the event.
- Serious adverse events will be captured from the time of the first protocol-specific intervention, unless the protocol states otherwise, and be reported until 30 days after the last protocol specific data collection timepoint. Serious adverse events must be followed until clinical recovery is complete and standard of care laboratory tests have returned to baseline, progression of the event has stabilized, or there has been acceptable resolution of the event.
- Additionally, any serious adverse events that occur after the 30 day time period, or protocol specific timeline, that are related to the study treatment must be reported to the IRB Office.

c. Data Safety Monitoring Board

Safety oversight will be provided by a DSMB. The DSMB consists of 5-7 expert members and are independent of study personnel. The DSMB will consist of members with expertise related to the trial. The DSMB will be run via teleconference with the following current members: [name] (pulmonologist, BCM), [name] (infectious disease physician, BCM), [name] (oncologist and immunotherapy expert, MD Anderson), [name] (infectious disease physician, BCM) and [name], an expert in mycobacterial infections and statistical design and evaluation. If these existing members are unable to participate, they will be replaced with another member with similar expertise. The DSMB will review study collected data and events every month including enrollment, demographics, compliance, adverse events. The DSMB can also meet ad hoc in the event of an unanticipated SAE. The DSMB independent study statistician, [name], will have access to unblinded study data to evaluate these criteria. A final data review meeting will occur two to four months after study completion to review the cumulative safety data. Additional data can be requested by the DSMB as they deem requisite. The DSMB may share de-identified reports with participating/collaborating sites and/or institutions.

d. Halting Rules

The DSMB or study PI may halt the study in for the following reasons:

- Two or more participants develop anaphylaxis
- Three or more participants develop disseminated BCG or suppurative lymphadenitis
- Three or more participants develop disseminated BCG-ititis

- Any participant experiences a serious unexpected adverse event that could be related to vaccination
- A 5% increase in severe COVID19 related illness (severe pneumonia, respiratory failure, ARDS, sepsis, septic shock) among those vaccinated compared to those that received placebo

e. Annual safety report

In addition to the expedited reporting of SUSARs, the Investigator will submit, a summary of safety reports to their IRB, annually, per their local policy and institutional guidelines..

f. Follow-up of adverse events

All AEs will be followed until they have abated, or until a stable situation has been reached. Depending on the event, follow up may require additional tests or medical procedures as indicated, and/or referral to the general physician or a medical specialist. SAEs collection and reporting will occur until end of study, as defined in the protocol.

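### The protocol gives two rules for taking the rt-PCR swab behind the primary endpoint, with no order of precedence, and the named survey symptoms omit loss of smell and taste

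*Combined protocol and SAP*

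**What the plan says.** The swab rule appears in several places.

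- **Section 7.c (follow-up procedures):** "Any positive response on the survey will trigger a nasopharyngeal, oral and/ or rectal swab to be collected to test for Covid-19 via rt-PCR". The survey goes to participants every 7 days.
- **Section 7.a (recruitment, randomization, blinding):** participants who develop symptoms after enrollment are handled differently: "they will be tested for COVID19 like any other health care worker or community member", and this happens "under the supervision, provisions and regulations of their institution and followed per protocol".
- **Section 7, Informed Consent and Eligibility:** swabs are "collected for rt-PCR test for SARS-CoV2 infection if a participant develops symptoms consistent with Covid-19". Section 7.c repeats this in similar terms, and section 3.a simply says that participants with symptoms will be tested. None of these defines the qualifying symptoms.

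The survey is meant "to assess the presence of any flu-like symptom, including sore throat, fever, headache, malaise, and cough". The same five symptoms carry the asterisk in the section 7.c data table. A catch-all field for other Covid-19 symptoms stands in that table without the asterisk, among the illness-course items, and is not said to trigger a swab. The rationale for the cognition sub-study, printed at the end of section 7, argues that the virus affects the nervous system, "as evidenced by the loss of smell and taste reported by many patients".

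Two further statements bear on the consequence. Section 7.c gives everyone serology at 4-week intervals whatever their survey answers. Section 6.a defines the primary endpoint by rt-PCR alone, while section 10.c reports participants who are PCR-positive or seroconvert.

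**The concern.** The two rules can select different people. Under section 7.c, a teacher who reports a headache is swabbed. Under section 7.a, what happens to that teacher depends on what the local institution or community offers. Two sites could each follow the protocol faithfully and swab different sets of participants.

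Section 4.b admits teachers, police, wait-staff, delivery personnel and the elderly as well as health care workers, and section 4.d foresees further sites. The protocol does not say which institution's regulations apply to a delivery worker. If section 7.a were followed, capture could vary with local policy and occupation.

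The symptom list raises a second, smaller gap. A trigger that works through survey answers needs an item to answer. A participant whose only symptom is loss of smell or taste has no named item.

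At stake is the number of primary events. An rt-PCR event that was never swabbed cannot be recovered at analysis. The secondary endpoint depends on the same swab, because section 6.b takes severity among those who test positive.

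**Working it through.** **1. The rules side by side**

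| Place | Who is swabbed | Who decides |
|---|---|---|
| 7.c | Anyone with any positive survey answer | The study |
| 3.a; 7, Informed Consent and Eligibility; 7.c (later paragraph) | Anyone with symptoms, or with symptoms consistent with Covid-19 | The study, by implication |
| 7.a | Symptomatic participants, as any other health care worker or community member | The participant's institution |

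The first two rows are compatible in spirit. The third is not tied to them, and no passage ranks them.

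**2. Inputs for the size**

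From section 10.a: 700 per arm, relative risk 0.4, two-sided type 1 error 0.05, planned power 80%, and 5% expected to develop symptomatic disease. I read 5% as the placebo rate, so BCG is 0.4 × 5% = 2%. The documents give no capture share *s* (the fraction of true cases that are swabbed and counted), so *s* is an assumption, taken as equal in both arms.

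**3. The plan's own figure**

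Power for two proportions with a pooled test, n per arm:

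power = Φ[(d − 1.96 × SE0) / SE1], where d = p1 − p2, SE0 = √(2 p̄(1 − p̄)/n), SE1 = √((p1(1 − p1) + p2(1 − p2))/n).

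With p1 = 0.05, p2 = 0.02, n = 700: d = 0.03, SE0 = 0.00982, SE1 = 0.00979, so power = Φ(1.10) = 86.4% (82.9% with continuity correction). The stated 80% would need 588 per arm (653 corrected). The plan's 700 does not reproduce, but it errs on the large side. That is a separate matter; here it only means that there is some headroom.

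**4. Effect of incomplete capture**

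Replace p1 by 0.05*s* and p2 by 0.02*s*. Expected events are 700 × 0.07 × *s* = 49*s*.

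| Capture *s* | Expected events | Power |
|---|---|---|
| 100% | 49 | 86.4% |
| 90% | 44 | 82.5% |
| 85% | 42 | 80.2% |
| 80% | 39 | 77.7% |
| 70% | 34 | 72.0% |
| 50% | 24.5 | 57.2% |

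Power crosses 80% at *s* of about 85% (about 93% with continuity correction).

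**5. Sensitivity**

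- The planned analysis is a Cox model. Schoenfeld's event formula gives 89.4% power at 49 events, 81.8% at *s* = 80% and 79.3% at *s* = 75%, so the crossing lies between 75% and 80%.
- If 5% is the rate over both arms together, the placebo rate is 0.05 × 2/1.4 = 7.14% and the BCG rate 2.86%. Power at full capture is then 95.8%, and the same formula crosses 80% only at *s* of about 59%.

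**6. Bias**

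The expected relative risk is 0.02*s* / 0.05*s* = 0.40 at every *s*. Unevenness across sites does not change this if the arms are balanced. With half the sample at *s* = 1.0 and half at 0.6, mean capture is 0.8, power is 77.7% and the relative risk is still 0.40.

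**The case against.** The strongest reply is that the protocol mostly agrees with itself. Section 3.a, the Informed Consent and Eligibility text and two places in section 7.c all promise a swab on symptoms. The section 7.a sentence stands alone, in a paragraph about avoiding transmission at enrollment. It says participants will be tested, expressly covers community members, and ends by saying they are followed per protocol. It can be read as saying where and under whose supervision testing happens, with the study swab alongside. That reading is possible. It is not stated, and the same sentence places testing under the institution's regulations, so the ambiguity stands.

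On symptoms, the list is introduced as open-ended, the survey form itself is not in the documents, and the looser symptom rules do not depend on a survey item. So the omission is from the named items. It does not prove that such a participant would go untested.

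On consequence, 4-weekly serology can recover many missed cases if the section 10.c definition governs. That is right, and it makes the size of the problem depend on the unresolved difference between sections 6.a and 10.c. Serology would still date an infection only to within about four weeks.

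A reader might also take "rt-PCR test results if done", in the follow-up data, as a sign that testing is discretionary. It is not. A symptom-triggered test is naturally absent in participants without symptoms, and the phrase fits section 7.c as it stands. Nor do the references to routine surveillance of health workers limit the trial survey to them; the survey is given to participants generally.

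**Conclusion.** The inconsistency is real and concerns how primary events are found, so it should be settled. Its size is conditional. With 5% v. 2% true rates, 700 per arm and loss equal between arms, power falls below the planned 80% once capture is under about 85%. The crossing moves to about 93% with continuity correction, to between 75% and 80% on the event-based formula, and to about 59% if 5% is the overall rate. The capture share is assumed throughout. The loss applies fully to the rt-PCR endpoint of section 6.a and less to the section 10.c definition.

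Two stronger readings are not supported:

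- **That infections are being missed unevenly by site and occupation.** The documents show rules that would permit this. They show no missed infections and no differing site policies.
- **That the efficacy estimate is biased.** Bias needs capture to differ between arms. Section 9.b says almost all BCG recipients develop a local reaction, so some participants might guess their arm, and this could affect test-seeking. As an illustration only, capture of 80% in BCG and 90% in placebo turns a true efficacy of 60% into 1 − 0.4 × 0.8/0.9 = 64%; the reverse gives 1 − 0.4 × 0.9/0.8 = 55%. Nothing in the documents shows such a difference.

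**What to change.** 1. Amend section 7.a so that the survey trigger of section 7.c governs the study swab for every participant, health care worker or not. State that institutional or community testing is in addition to that swab and does not replace it.
2. Add *new loss of smell or taste* to the weekly survey items in section 7.c and to the data table there, marked as a swab trigger. It is the one symptom that the protocol itself already attributes to many patients.
3. Reconcile sections 6.a and 10.c, so that it is clear whether seroconversion without a positive swab counts as a primary event.

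The first two changes are a sentence and a survey item. The added symptom brings a few more swabs of a kind already planned. The third is a wording decision that the analysis needs in any case.
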